12.5 Safety Analyses

We will assess for the system's functionality, including the ability of the system to run its code without errors (delivering insulin safely), as well as its ability to avoid low BGs <70 mg/dL.

12.6 Criteria for Success

The success criteria will include no critical system errors and the following performance criteria, which factor in likely inter-day variability for each participant and are consistent with the recommendations of the International Consensus on TIR:

- Positive difference in TIR between AIDANET+BPS_RL and AIDANET, e.g. TIR on AIDANET+BPS_RL greater than TIR on AIDANET, regardless of p-value;
- Difference in TBR between AIDANET+BPS_RL and AIDANET < 3 percentage points;
- Positive difference in TAR between AIDANET+BPS_RL and AIDANET.

Formal power analysis is not applicable to this pilot study – with this sample size a statistically significant result is not expected (Power less than 50%). The point of the study is to show feasibility of the new BPS and assess whether effect size $f=0.2$ is achievable in a subsequent study.

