As the Principal Investigator, I will assure that no deviation from, or changes to the protocol will take place without prior agreement from the sponsor and documented approval from the Institutional Review Board (IRB), or other approved Ethics Committee, except where necessary to eliminate an immediate hazard(s) to the trial participants.

All key personnel (all individuals responsible for the design and conduct of this trial) have completed Human Participants Protection Training and Good Clinical Practice Training. Further, I agree to ensure that all staff members involved in the conduct of this study are informed about their obligations in meeting the above commitments.

Investigator's Signature _____ Date: ____ / ____ / ____

Investigator's Name: _____

Site Name: University of Virginia

LIST OF ABBREVIATIONS

Abbreviation	Definition
ADA	American Diabetes Association
AE	Adverse Event
AID	Automated insulin delivery
AIDANET	Automated insulin delivery as Adaptive Network
AP	Artificial pancreas
AUC	Area Under the Curve
AYA	Adolescent and Young Adult
BDC	Barbara Davis Center
BG	Blood Glucose (as assessed by a blood glucose meter)
BGM	Blood glucose meter
BPS	Bolus Priming System
CGM	Continuous glucose monitor
CSII	Continuous subcutaneous insulin infusion
DiAs	Diabetes Assistant
DKA	Diabetic Ketoacidosis
DWM	DiAs Web Monitoring
FCL	Fully automated closed-loop
HbA1c	Hemoglobin A1c
HCL	Hybrid closed loop
NAP	Neural-network artificial pancreas
RL	Reinforcement Learning
SAE	Severe Adverse Event
SG	Sensor Glucose (as assessed by a continuous glucose monitor)
SH	Severe Hypoglycemia
T1D	Type 1 diabetes
TAR	Time above range
TBR	Time below range
TIR	Time in range 70-180 mg/dL

PROTOCOL SUMMARY

Participant Area	Description
Title	Safety and Feasibility of a Machine-Learning Bolus Priming Added to Existing Control Algorithm (AIDANET)
Investigational Device	Reinforcement Learning trained Bolus Priming System (BPS_RL) added to the AIDANET algorithm and running on DiAs phone wirelessly connected to Tandem t:AP insulin pump and Dexcom CGM
Objectives	The primary objective of the project is to demonstrate feasibility and safety of the BPS_RL added to the existing AIDANET AID algorithm, used in FCL mode by adults with T1D.

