10.9 Stopping Criteria

10.9.1 Participant Discontinuation

A participant will be discontinued if any of the following occur:

- The Study Physician believes it is unsafe for the participant to continue the intervention. This could be due to the development of a new medical condition or worsening of an

-
- 1105 existing condition; or participant behavior contrary to the indications for use of the device
1106 that imposes on the participant's safety
- 1107 • The participant requests that the treatment be stopped
 - 1108 • Two distinct episodes of DKA
 - 1109 • Two distinct severe hypoglycemia events as defined in section 10.2.1.
 - 1110 • Two events of any kind: severe hypoglycemia or DKA

1111 **10.9.2 Suspending/Stopping Overall Study**

1112 In the case of an unanticipated system malfunction resulting in a severe hypoglycemia or severe
1113 hyperglycemia event (as defined in section 10.2.2), use of the study device system will be
1114 suspended while the problem is diagnosed.

1115 In the event that two distinct episodes of DKA or two distinct severe hypoglycemia events as
1116 defined in section 10.2.1 occur, the overall study would be suspended while the underlying
1117 conditions are determined.

1118 In addition, study activities could be similarly suspended if the manufacturer of any constituent
1119 study device requires stoppage of device use for safety reasons (e.g., product recall). The affected
1120 study activities may resume if the underlying problem can be corrected by a protocol or system
1121 modification that will not invalidate the results obtained prior to suspension. As previously noted,
1122 the Study Physician will review all adverse events and adverse device events that are reported
1123 during the study. The Study Physician may request suspension of study activities or stoppage of
1124 the study if deemed necessary based on the totality of safety data available.

1125 **10.10 Definition of a Data Breach**

1126 A data breach is defined in the HITECH Act (43 USC 17932) as an unauthorized acquisition,
1127 access, or use of protected health information (PHI) that compromises the security or privacy of
1128 such information.

1129 **Chapter 11: Miscellaneous Considerations**

1130 **11.1 Prohibited Medications, Treatments, and Procedures**

1131 Participants using glulisine at the time of enrollment will be asked to contact their personal

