12.3 Outcome Measures

The primary outcome will be the CGM-measured time in range (TIR, 70-180 mg/dL) during the 18-hour hotel sessions on AIDANET or AIDANET+BPS_RL (Figure 1). The time periods begin at 6 PM and end at noon on the next day, thereby covering two meals – dinner and breakfast. These

time periods are expected to reflect well any differences, e.g., potential TIR improvement, that can be attributed to the new BPS_RL.

Secondary outcomes from the 18-hour Hotel Sessions of the study (see Figure 1):

Descriptive glycemic analyses for certain efficacy measures recommended by the International Consensus on TIR, to which we contributed, will be tabulated for each subject based on CGM data, including:

- percentage of readings in other ranges, including time below range (TBR, < 70 mg/dl), time above range (TAR, > 180 mg/dl) and time in tight range 70-140 mg/dl;
- mean glucose; glucose variability measured by coefficient of variation;
- percentage of readings <54 mg/dl (i.e., level 2 hypoglycemia)
- percentage of readings >250 and >300 mg/dl (i.e., level 2 hyperglycemia).

Secondary outcomes from the 1-week Home Sessions of the study (see Figure 1):

All CGM-based glycemic metrics computed during the Hotel sessions of the study will be computed during the Home sessions as well. *The last 3 days of each week at home on AIDANET or AIDANET+BPS_RL will be used for the analyses described below.*

We will also observe, record, and tabulate any system errors that would inform us whether system fixes would be needed prior to deployment in a subsequent larger study. We will tabulate technical performance metrics including:

- Malfunctions requiring study team contact and other reported device issues;
- Percent time in closed-loop and any other relevant operational modes;
- Rate of relevant AIDANET+BPS_RL failure events and alarms per 24 hours;

The technical performance, errors, and glycemic analyses will be also split by time of the day: daytime vs. night-time.

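### Safety is a primary objective, yet severe hypoglycaemia and DKA play no part in the success criteria (12.6) or the safety analyses (12.5)

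*Combined protocol and SAP*

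**What the plan says.** The Protocol Summary states the aim: "The primary objective of the project is to demonstrate feasibility and safety of the BPS_RL added to the existing AIDANET AID algorithm". Sections 2.1 and 12.1 repeat it, and both aims in 2.2 name safety.

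Section 12.6 then sets the decision rule: "The success criteria will include no critical system errors and the following performance criteria". The performance criteria are three:

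- TIR: "TIR on AIDANET+BPS_RL greater than TIR on AIDANET, regardless of p-value"
- TBR: "Difference in TBR between AIDANET+BPS_RL and AIDANET < 3 percentage points"
- TAR: "Positive difference in TAR between AIDANET+BPS_RL and AIDANET"

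Section 12.5, Safety Analyses, is a single sentence. It covers whether the code runs without errors, "as well as its ability to avoid low BGs <70 mg/dL".

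Chapter 10 defines severe hypoglycaemia (10.2.1), DKA and reportable ketone events (10.2.2), SAEs (10.1.2), and adverse device effects, anticipated or not (10.1.3, 10.1.4). All are reported and reviewed by the Study Physician. Section 10.9.2 sets a study-level trigger: "In the event that two distinct episodes of DKA or two distinct severe hypoglycemia events as" defined in 10.2.1 occur, the whole study is suspended while the cause is investigated. It may resume if the problem can be corrected.

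Time below 54 mg/dL is a secondary outcome in 12.3, and 12.4 expects to test it with a paired Wilcoxon test. It has no threshold in 12.6. Section 12.3 also tabulates malfunctions, reported device issues and failure-event rates.

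**The concern.** The events that the protocol itself treats as grave enough to halt the study do not enter the rule that decides whether the study succeeded. The new component is a learned calculation of the priming bolus. Its obvious hazards are a bolus that is too large and a failure to deliver enough insulin. Severe hypoglycaemia and DKA are the clinical end of those two hazards.

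If the listed criteria can all be met in the presence of such events, the rule does not answer the safety half of the primary objective. How much weight a severe event carries would then be settled after the data are seen. Section 12.2 says that pilots of this kind support regulatory approval of larger studies, and it already names a follow-on study of N=50, so the success claim has consequences.

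**Working it through.** **Inputs from the documents.** The TBR limit is 3 percentage points (12.6), and TBR is time below 70 mg/dL (12.3). The hotel window is 6 PM to noon, 18 h = 1080 min (12.3). The home window is the last 3 days of each week, 72 h = 4320 min (12.3). Completers are 16 in the Protocol Summary and 15 in 12.2. The study-level trigger is two DKA episodes or two severe hypoglycaemia events (10.9.2).

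**Assumptions, not in the documents.** Each event lasts 60 min below 70 mg/dL (range 30 to 120). Both events occur on AIDANET+BPS_RL and none on AIDANET. The TBR difference is a difference in group means over full windows. Section 12.6 states neither the summary measure nor whether the hotel or the home window applies.

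**Step 1: what 3 points means.** 0.03 × 1080 = 32.4 min per participant per hotel session, or 32.4 × 16 = 518.4 min across 16 participants.

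**Step 2: effect of two severe lows on group-mean TBR.** Added points = 100 × (events × minutes) / (N × window minutes).

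| Minutes per event | Hotel, N=16 | Hotel, N=15 | Home 72 h, N=16 |
|---|---|---|---|
| 30 | 0.35 | 0.37 | 0.09 |
| 60 | 0.69 | 0.74 | 0.17 |
| 120 | 1.39 | 1.48 | 0.35 |

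For example, 100 × (2 × 60)/(16 × 1080) = 0.69. With no other TBR difference, each of two events would have to last 518.4/2 = 259 min at the hotel to reach the limit. At home the figure is 0.03 × 4320 × 16/2 = 1037 min.

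**Step 3: the per-participant reading.** If the limit applied to each person, one 60-min hotel event would be 60/1080 = 5.56 points in that person. That breaches the limit unless TBR on AIDANET was also high. This reading still misses lows shorter than 32.4 min, any home event before the last 3 days, and DKA.

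**Step 4: DKA.** It does not raise TBR. Read literally, the TAR criterion rewards a rise in TAR and so puts no ceiling on hyperglycaemia. If a fall in TAR was meant, hyperglycaemia inside the window would count against success. Even a whole hotel session above 180 mg/dL in one of 16 participants moves the group mean by at most 100/16 = 6.25 points, and gains in the other 15 can offset that. On either reading the event itself is not a criterion.

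**Step 5: rules that can remove the CGM trace of an event.** Section 6.6.1 discharges a participant after severe hypoglycaemia. Section 11.2 leaves use of withdrawn participants' data to the study team. Section 12.7 deletes CGM values within 2 h of a recorded occlusion. Home metrics use only the last 3 days.

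**Step 6: what event counts can show.** For 0 of 16, the exact two-sided 95% upper limit is 1 − 0.025^(1/16) = 20.6%. For 2 of 16 (12.5%), the exact interval is 1.6% to 38.3%.

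**The case against.** Much can be said for the plan.

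- **Chapter 10 governs safety.** The Study Physician reviews each event form, UADEs go to the FDA, and the study can be suspended or stopped on all the safety data. A reader might infer that severe events would go unreported or unmanaged; the documents do not support that. This point stands, but it concerns protection during the trial. Nothing carries a Chapter 10 event into the success decision.
- **Time below 54 mg/dL and device effects are in the plan.** A reader might infer that they are absent altogether. They are not: time below 54 is a tested secondary outcome (12.3, 12.4), ADEs and UADEs are reported under 10.7 with listed exceptions, and device issues are tabulated under 12.3. They are missing only from the decision. There is no explicit table of severe hypoglycaemia, DKA or SAEs.
- **The 12.6 list may be open-ended, and it is labelled as performance.** A reader might infer that passing 12.6 is the safety verdict offered to regulators. No section says so. But if the list is open-ended, the weight given to a severe event is unstated.
- **A harmful bolus might count as a critical system error.** Critical is undefined, and 12.5 links error-free running to safe insulin delivery. One therefore cannot say that such an event is excluded, only that the text does not include it.
- **The size rests on assumptions.** The duration and the group-mean reading are not in the documents, and a discharged participant's session may be cut short. That is fair. Steps 3 and 4 show that the gap narrows under the other reading but does not close.
- **A zero-event rule has low power to reassure.** With 16 participants this is true, and it is a reason to report confidence limits alongside the count.

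**Conclusion.** The point holds in a limited form and should be fixed. Neither 12.5 nor 12.6 uses severe hypoglycaemia or DKA, so the listed criteria can all be met after device-related events that would have suspended the study under 10.9.2. On a group-mean TBR with 16 participants and an assumed 60 min per event, two severe lows at the hotel use 0.69 of the 3 points allowed (0.35 to 1.39 for 30 to 120 min). DKA uses none.

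The omission is a matter of text and needs no assumption. The figures depend on event duration, N, full windows, no offsetting TBR difference and the group-mean reading. Success after such events is possible, not certain: the TIR criterion could fail for the same reason, a malfunction could be classed as a critical error, and a suspended study might not resume. The finding is about the decision rule, not about participant monitoring.

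**What to change.** **In 12.6:**

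- Add that success is not claimed if severe hypoglycaemia (10.2.1) or DKA (10.2.2), judged at least possibly related to the device on the 10.3 scale, occurs on AIDANET+BPS_RL at the hotel or at any time in the home week.
- State how a suspension under 10.9.2 affects the success claim.
- Reconcile the event count used in this criterion with the two-event trigger in 10.9.2, so that the two rules are deliberately related.
- State whether the TBR difference is a group mean or per participant, and which window it covers.

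**In 12.5:**

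- Tabulate severe hypoglycaemia, DKA, reportable ketone events, SAEs and ADEs/UADEs by the algorithm in use at onset, with exposure time and exact confidence limits.
- Include everyone exposed, with discharged and withdrawn participants counted whatever is decided about their CGM data under 11.2.

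Separately, 6.6.1 discharges a participant after one severe event while 10.9.1 discontinues after two. These passages must be reconciled, since they determine who contributes data.

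**Cost.** A few lines of text. The events are already collected under Chapter 10. Success becomes slightly harder to claim, and with 16 participants a clean record still leaves an upper limit of 20.6%, which the report should state.

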2.2 Specific Aims and Hypotheses

Aim 1: To evaluate the performance (safety, efficacy) of AIDANET+ BPS_RL used as FCL.

Hypothesis: AIDANET+ BPS_RL use will result in equivalent or better Time in Range (TIR) than AIDANET (including current BPS) during two 18-hour hotel sessions (randomized crossover).

[figure not shown]
Aim 2: To evaluate the safety and efficacy of AIDANET+ BPS_RL at home.

Hypothesis: AIDANET+ BPS_RL use will result in equivalent or better TIR than AIDANET alone, during a week of At-Home use (repeated measures).

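### As written, the TAR success criterion in section 12.6 is met only if the new bolus system increases time above 180 mg/dL

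*Combined protocol and SAP*

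**What the plan says.** Section 12.6 (Criteria for Success) asks for no critical system errors and gives three performance criteria:

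- TIR: "Positive difference in TIR between AIDANET+BPS_RL and AIDANET, e.g. TIR on AIDANET+BPS_RL greater than TIR on AIDANET, regardless of p-value".
- TBR: "Difference in TBR between AIDANET+BPS_RL and AIDANET < 3 percentage points".
- TAR: "Positive difference in TAR between AIDANET+BPS_RL and AIDANET".

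Section 12.3 (Outcome Measures) defines the three ranges: "CGM-measured time in range (TIR, 70-180 mg/dL"), "time below range (TBR, < 70 mg/dl") and "time above range (TAR, > 180 mg/dl"). Section 2.2 gives the Aim 1 hypothesis: "AIDANET+ BPS_RL use will result in equivalent or better Time in Range (TIR) than AIDANET (including current BPS").

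No section says that positive means favourable, or that the subtraction is reversed for TAR.

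**The concern.** The TIR bullet explains its own phrase: "TIR on AIDANET+BPS_RL greater than TIR on AIDANET, regardless of p-value". The TAR bullet uses the same phrase with the two systems in the same order. Read consistently, it rewards more hyperglycaemia.

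The module under test sets priming boluses for meals (Chapter 1), and the 18-hour window was chosen to span dinner and breakfast (section 12.3). Less time above 180 mg/dL after meals is the natural way for such a module to raise TIR, and that is the result the bullet rejects.

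Section 12.6 sets significance aside, so the sign of each point estimate is the decision rule. Correcting a sign after the results are known would be a post-hoc change to a success criterion.

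**Working it through.** **Inputs.** The three criteria come from section 12.6 and the range definitions from section 12.3. The number of completers is 16 (synopsis and section 3.2); section 12.2 says 15. The documents give no SD for any paired difference, so every SD, correlation and true effect below is an assumption.

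**The plan's own figure.** The TAR bullet has no figure to reproduce. Section 12.6 does state power below 50%. Taking f = 0.2 and an assumed within-person correlation of 0.5, dz = 2f/√(2(1−ρ)) = 0.4/1 = 0.40. A two-sided 5% paired t-test then has power 0.32 at N = 16, which agrees. Over assumed correlations of 0, 0.7 and 0.8 the power is 0.19, 0.49 and 0.66. None of this depends on the TAR bullet.

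**Step 1: the identity.** The ranges below 70, 70 to 180 and above 180 mg/dL cover all readings, so TBR + TIR + TAR = 100% on each system. Write d for the mean on AIDANET+BPS_RL minus the mean on AIDANET. Then dTIR + dTBR + dTAR = 0.

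**Step 2: the criteria as written.** If dTIR > 0 and dTAR > 0, then dTBR = −(dTIR + dTAR) < 0. The fall in TBR also exceeds the rise in TIR, because −dTBR = dTIR + dTAR > dTIR. Any result that meets the TIR and TAR bullets therefore already has dTBR below 0, and the limit of 3 points adds nothing.

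**Step 3: examples, in percentage points.**

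| dTIR | dTBR | dTAR | As written | TAR sign reversed |
|---|---|---|---|---|
| +5 | 0 | −5 | fails | passes |
| +5 | +2 | −7 | fails | passes |
| +5 | −1 | −4 | fails | passes |
| +1 | −2 | +1 | passes | fails |

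On a grid of dTIR and dTBR from −10 to +10 in steps of 0.5, 520 points meet the TIR and TBR bullets. Of these, 190 also meet the TAR bullet as written, 310 meet it with the sign reversed, and 520 − 190 − 310 = 20 have dTAR exactly zero.

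**Step 4: illustration of size.** Group-mean differences were simulated as bivariate normal with N = 16, so each standard error is SD/√16 = SD/4. The SD of the paired TBR difference was 3 points and the correlation between the TIR and TBR differences was −0.2. The table gives the chance of meeting all three performance criteria.

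| True dTIR | True dTBR | SD of TIR difference | As written | Sign reversed |
|---|---|---|---|---|
| +5 | 0 | 12 | 0.8% | 94% |
| +5 | 0 | 8 | 0.2% | 99% |
| +5 | 0 | 15 | 1.1% | 90% |
| +5 | −1 | 12 | 4% | 91% |
| +5 | −2 | 12 | 11% | 85% |
| +2 | −1 | 12 | 12% | 63% |
| +2 | −2 | 12 | 25% | 50% |

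With N = 15 the first row becomes 0.9% and 94%.

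**The case against.** The best defence is that this is a slip which nobody would apply literally. Positive may have been meant as favourable, and section 12.6 says its criteria follow the international consensus on TIR. That is plausible, and a real TIR gain may well not be called a failure in practice. But the only explanation of the phrase in the document points the other way, so the text needs correcting.

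Three further objections stand in part:

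- Section 12.6 says that the success criteria include these items; it does not say that all must be met. Joint application is the natural reading, but it is a reading. Taken alone, the TAR bullet still asks for higher TAR.
- The identity is exact for means. Section 12.4 allows a signed-rank comparison of medians for skewed outcomes, and median differences need not sum to zero. Section 12.6 does not name the summary to be used.
- The probabilities rest on assumed inputs and move considerably with them. The evidence is the algebra; the simulation only illustrates it.

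A reader might also infer more than the documents support:

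- *That protection against hypoglycaemia is lost.* It is not. The literal criteria force mean TBR down, which is stricter than the 3-point allowance. Section 12.5 assesses low glucose separately, and the stopping criteria in section 10.9 do not use section 12.6.
- *That any algorithm working as intended must fail.* The stated hypothesis concerns TIR, and no section names lower TAR as the aim. A TIR gain obtained through a larger cut in TBR, such as (+1, −2, +1), passes.
- *That these bullets are the whole of the success rule.* The absence of critical system errors is also required.

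**Conclusion.** Wrong as written. The TAR bullet is met only when time above 180 mg/dL is higher on AIDANET+BPS_RL. If the criteria are applied jointly and to means, success requires TBR to fall by more than TIR rises, a TIR gain that comes from less time above range fails, and the TBR bullet is redundant. That result needs no assumed SD or effect size.

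In the scenarios shown, the chance of meeting all three criteria is about 0.2% to 25% as written and about 50% to 99% with the sign reversed. The primary outcome, the primary analysis, the sample size and the power statement are unaffected.

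**What to change.** Change the third bullet of section 12.6 to: *Negative difference in TAR, i.e. TAR lower on AIDANET+BPS_RL than on AIDANET.* State once that all differences are AIDANET+BPS_RL minus AIDANET.

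The sponsor should also confirm two things that section 12.6 leaves open: whether the criteria apply to the hotel sessions, the home weeks or both, and whether all of them must be met using means.

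The 3-point TBR limit then has force again. The reversed TAR bullet will follow automatically from dTIR > 0 whenever TBR does not fall, so it adds a separate requirement only when TBR falls; it would reject (+1, −2, +1). The sponsor should confirm that this is wanted.

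The cost is a wording amendment to one section, with no change to trial conduct, data collection or sample size. It should be made before outcome data are examined.
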